Title: Optimal timing of a second post-operative voiding trial in women with incomplete bladder emptying after vaginal reconstructive surgery: A randomized trial

NCT 03048682

Date: 12/1/2018

Title: Optimal timing of a second post-operative voiding trial in women with incomplete bladder emptying after vaginal reconstructive surgery: A randomized trial

Principal Investigator, Co-investigator(s): [name], [name], [name], [name], [name], [name]

Sponsor or funding source: N/a

Background, Rationale and Context

Postoperative voiding trials (VT) are performed after reconstructive pelvic surgery due to the heightened risk of transient urinary retention. Studies have reported rates of post-operative urinary retention following surgery for vaginal prolapse ranging from 6-29%, higher than after vaginal hysterectomy for non-prolapse indications. Patients who are unable to successfully void after surgery may be discharged home with an indwelling transurethral catheter for several days until a voiding trial may be repeated in the office. Indwelling catheters are associated with an increased risk in urinary tract infection (UTI), increased discomfort and poor patient satisfaction. It has been shown that duration of catheterization is the most important determinant of developing bacteriuria. Several studies have been performed comparing the length of time a Foley catheter is left in place after a gynecologic surgery. Overall, earlier catheter removal reduces rates of UTI, but has been associated with a higher risk of urinary retention and re-catheterization. VTs aid in the decision-making process as to whether or not a patient is a candidate for early discontinuation of a Foley catheter. With the recent trend toward minimally invasive and outpatient surgeries, patients are frequently discharged home on the day of surgery. In such cases, patients undergo a voiding trial in the recovery room on the same day of surgery, prior to discharge. Patients who are successfully able to empty their bladders may be discharged without a catheter. Those who are unsuccessful have a Foley catheter re-inserted and are discharged with an appointment scheduled for an office voiding trial. The length of time to repeat a voiding trial after an initially failed trial has yet to be studied.

Objectives

Primary Objective

The primary objective of this study is to determine the timing to return to normal bladder function after pelvic floor reconstructive surgery for those patients who failed the initial post-operative VT. To assess this, the rate of failure of repeat VT will be assessed at two post-operative time points.

Secondary Objectives

To evaluate:

- The rates of UTI in the two groups
- Rates of Foley catheter re-insertion after passing a subsequent office void trial
- Patient Satisfaction

Methods and Measures

Design

This study is a randomized controlled trial designed to assess the timing of return to normal bladder function after pelvic floor reconstructive surgery. The primary outcome will be assessed by comparing office VT failure rates between those who return in the early post-operative period (2-4 days) vs the standard time to return for an office VT (1 week). Based on the Hakvoort et al

study and a 95 two-sided significance level and 80% power, this study would require 60 subjects, or 30 per group. Assuming a 10% drop-out rate, 66 total subjects should be enrolled in the study. All patients that meet the appropriate inclusion criteria will be considered for the study. OR schedules will be reviewed and subjects will be assessed for possible eligibility approximately 1-2 weeks prior to surgery. Patients will be counseled about the study either in the office during a surgical planning office visit, over a pre-operative telephone call, or in the pre-operative area just prior to surgery. Consents will be signed in the pre-operative area.

After surgery, the patient will be given a standardized voiding trial as per the usual protocol. If the patient is un-successful in emptying her bladder according to the VT protocol she will be discharged home with an indwelling Foley catheter as per usual protocol. On post-operative day (POD) #1 the patient will be re-assessed for meeting eligibility requirements. Once eligibility is established, the subject will be called on POD#1 and randomized to either the early voiding trial group (EVT) or the late voiding trial group (LVT). Subjects in EVT will be scheduled for a repeat VT on POD#2-4, whereas those in LVT will be scheduled for a repeat VT on or after POD#7. Subjects that are unsuccessful in the repeat VT will have a Foley catheter re-inserted and will return for another VT in 5-7 days. Subjects who fail the third VT from either group will have the Foley catheter replaced and will return for another office VT after waiting an additional 5-7 days or will be started on clean intermittent self-catheterization.

Subjects will be monitored for a 6 week period. During that time the patient will be monitored for voiding and urinary symptoms. Urine will be tested via in-office urinalysis at each office visit (as per usual practice), including pre-operatively, and will be sent for a urine culture per usual practice based upon abnormal urinalysis results (ie. any blood or leukocytes). Urine cultures that grow out a single organism >10,000 CFU will be treated with appropriate antibiotics. In addition, patients will complete quality of life questionnaires at the time of catheter removal and at 6weeks post-operatively.

Setting

The study will take place at two medical centers. Most of the interactions will take place in the office setting, including all pre-operative evaluations, and post-operative follow-up. Surgeries will be performed in the hospital setting.

Subjects selection criteria

Inclusion Criteria

Subjects must meet the following inclusion criteria in order to be eligible for the study

- Female patients age 18 or older
- Speak English and are capable of giving informed consent
- Are willing to return to the office for all necessary visits associated with the study
- Underwent outpatient gynecology pelvic floor surgery for multi-compartment prolapse
- Failed the voiding trial in the recovery room on POD#0

Exclusion Criteria

Subjects must not have any of the following exclusion criteria in order to be eligible for the study

- Pre-operative urinary retention as defined as PVR > 200ml
- Prior incontinence surgery
- Passed the voiding trial in the recovery room

- Require prolonged catheterization due to urethral/bladder abnormality (ie vesicovaginal fistula, urethral diverticulum) or intra-op urethral or bladder injury or for intensive post-operative monitoring
- Patients who take any post-operative antibiotics, other than prophylaxis during catheterization, for reasons other than a UTI as diagnosed and prescribed as part of the study
- Patients who take any supplements to prevent UTIs, including but not limited to D-Mannose, Hiprex, or Ellura
- Have any neurological conditions that may affect bladder function (ie. Multiple sclerosis, spinal cord injuries, etc.)
- Patients with pre-operative narcotic medication use due to chronic pain

• Sample Size

Using OpenEpi.com and the Fleiss statistical method the sample size was calculated for a randomized controlled trial based on the Hakvoort et al. study. With a 95% two-sided significance and an 80% power, this study will need 60 subjects to be adequately powered to test for the primary outcome of differences in Foley catheter re-insertion rates.

• This is a multi-center study. The coordinating institution is the Cleveland Clinic Florida in Weston, FL. The study has been approved and enrollment is underway at that site. Over 30 patients are already enrolled at that site. Ideally, 20 subjects would be enrolled from Wake Forest Baptist Health in North Carolina.

Interventions and Interactions

- As described above, if the patient does not pass the recovery room VT, a Foley catheter will be inserted for either 2-4 or 7 days depending on the randomization. Prophylactic antibiotics may be used per the surgeon's preference. Length of catheter duration will depend on when the patient is able to pass an outpatient VT.
- As described above, urine cultures will be performed as medically indicated. A single identified organism of 10,000 CFU or greater will be considered a positive culture.
- Pre-operative and post-operative questionnaires will be used to assess patient satisfaction with their voiding/ Foley catheter use.
- Office notes will be reviewed to assess for study eligibility. Background data will be
 collected for descriptive statistics. Data from urodynamic studies will also be collected as part
 of the background data. Post-operative notes from the clinic will be reviewed to assess for
 any complications or adverse events. Surgical and hospital records will be reviewed and
 various data will be collected to ensure that there was equivalence in the groups for items
 such as: type of surgery, post-op narcotic use, length of surgery, time to recovery room void
 trial, etc.

Length of time spent by each subject on specific study materials will only include the length of time to complete the short questionnaires. The remainder of their care, including surgery, post-operative follow-up, repeat VT are part of the usual post-operative care

			Visit			
	Pre-Study	Recovery Room	V#1 (Repeat VT, either POD 2-4 or 6-7)	V#2 (Repeat VT if failed at V#1 Or 2 week post- op visit)	V#3 (2 week routine post-op visit or 6 week post- op visit)	V#4 (6 week post-op visit, if not completed at V#3)
Informed Consent	X					

Demographics	X					
Medical History	X		X	X	X	X
Physical Exam	X			X	X	X
Pre-operative Labs	X					
Urodynamic	X					
Testing	Λ					
Voiding Trial		X	X	X		
Patient	v		X	v	v	v
Questionnaire	Λ		Λ	Λ	Λ	Λ
Urine Sample	X		X	X	X	X

Outcome Measure(s)

• Outcomes that will be assessed include: void trial outcomes, UTI rates, urinary retention rates, and patient satisfaction.

Human Subjects Protection

Subject Recruitment Methods

Upcoming surgical schedules will be reviewed 1-2 weeks prior to surgery. Patients will be contacted by a member of the study team to discuss eligibility, review the inclusion/exclusion criteria, and to answer all questions. Consent will be signed prior to surgery. Any subject who wishes to withdraw from the study may do so at any time. When the subject chooses to withdraw, they will be presented with the option to either allow all of the data collected to that point be retained, or if they would like it to be removed.

All data will be kept on secure password protected and encrypted hospital computers and contained within password protected files. Source documents will be kept in a locked drawer on hospital property. Protected health information will be de-identified.

Informed Consent

Signed informed consent will be obtained from each subject. Consent will be obtained by one of the study staff prior to surgery.

Confidentiality and Privacy

Confidentiality will be protected by collecting only information needed to assess study outcomes, minimizing to the fullest extent possible the collection of any information that could directly identify subjects, and maintaining all study information in a secure manner. To help ensure subject privacy and confidentiality, only a unique study identifier will appear on the data collection form. Any collected patient identifying information corresponding to the unique study identifier will be maintained on a linkage file, store separately from the data. The linkage file will be kept secure, with access limited to designated study personnel. Following data collection subject identifying information will be destroyed seven years after the conclusion of the study consistent with data validation and study design, producing an anonymous analytical data set. Electronic data will be permanently deleted and source documents will be shredded using the hospital system. Data access will be limited to study staff. Data and records will be kept locked and secured, with any computer data password protected. No reference to any individual participant will appear in reports, presentations, or publications that may arise from the study.

Data and Safety Monitoring

The principal investigator will be responsible for the overall monitoring of the data and safety of study participants. The principal investigator will be assisted by other members of the study staff.

Reporting of Unanticipated Problems, Adverse Events or Deviations

Any unanticipated problems, serious and unexpected adverse events, deviations or protocol changes will be promptly reported by the principal investigator or designated member of the research team to the IRB and sponsor or appropriate government agency if appropriate.

References

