Title: Optimal timing of a second post-operative voiding trial in women with incomplete bladder emptying after vaginal reconstructive surgery: a randomized trial

NCT: NCT03048682 **DATE**: December 15, 2018

Statistical Analysis Plan

Descriptive statistics were calculated for the overall sample. The data was assessed using an intention-to-treat analysis. Continuous data with normal distribution were analyzed using Student's t-test, whereas skewed data were analyzed using a Wilcoxon signed-rank test. Categorical data, such as void trial failure rates (the primary outcome), were analyzed using Pearson's chi-square test or Fisher's exact test if there were ≤5 subjects in 20 % of the cells. Patients bother as noted on a Likert scale was considered as ordinal data. Univariate analysis as well as a forward stepwise multivariate regression analysis were performed. A p-value of less than 0.05 was considered statistically significant. All analyses were performed using JMP version 14.0.0 (SAS Institute Inc., Cary, NC).

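### The primary objective asks when normal voiding returns, but its only planned comparison is failure of one repeat voiding trial held on different days in the two arms; catheter days are not a named outcome

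*Protocol*

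**What the plan says.** The Primary Objective section of the protocol sets out to "determine the timing to return to normal bladder function after pelvic floor reconstructive surgery" in women who failed the first VT. It then says how: "the rate of failure of repeat VT will be assessed at two post-operative time points". The Design section repeats the aim and gives the comparison: "The primary outcome will be assessed by comparing office VT failure rates between those who return in the early post-operative period (2-4 days", with the other group returning at one week. The Sample Size section calls the same endpoint by its consequence: "adequately powered to test for the primary outcome of differences in Foley catheter re-insertion rates".

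On scheduling, Design states "Subjects in EVT will be scheduled for a repeat VT on POD#2-4" and places the late arm on or after POD 7. A woman who fails is re-catheterised and retested 5-7 days later. Follow-up lasts 6 weeks. Interventions and Interactions adds: "Length of catheter duration will depend on when the patient is able to pass an outpatient VT".

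The SAP names VT failure as the primary outcome and tests it by chi-square or Fisher's exact test. The secondary objectives are UTI, re-insertion after a passed office VT, and satisfaction; Outcome Measure(s) adds retention. Neither document names catheter days, day of first passed VT, or status on a common day, and no time-to-event method appears. The SAP's general provisions for continuous data and stepwise regression are not tied to any time outcome.

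**The concern.** A failure proportion at POD 2-4 set against one at about POD 7 shows how likely a VT is to fail on each day. It does not show which schedule frees women from the catheter sooner, which is what the objective and the title ask. Recovery accrues with time, so a later test has a built-in advantage on this endpoint. A woman who fails early and passes her retest may still finish close to when a late-arm woman has her first attempt, but the primary analysis counts her only as a failure.

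The protocol's own rationale makes this matter: Background names length of catheterisation as the leading driver of bacteriuria and links catheters to discomfort and dissatisfaction. If the primary test favours late VT, the plan has no named measure of catheter exposure to set beside it.

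**Working it through.** **1. The plan's own figure.** The protocol says: "With a 95% two-sided significance and an 80% power, this study will need 60 subjects", that is, 30 per group. No failure rates are given, so 60 cannot be reproduced. Solving the Fleiss formula backwards (two-sided 0.05, 80% power, no continuity correction), pairs that need about 30 per arm are 5% v 33%, 10% v 41%, 15% v 48% and 20% v 54-55%. With the correction, 10% pairs with 45%. Enrolment follows as 60 × 1.10 = 66. I use 41% v 10% as an assumed pair.

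**2. Power of the primary test at 41% v 10%.** Summing binomial probabilities over all 31 × 31 possible results with p < 0.05 gives 82% for chi-square and 73% for Fisher. In single results, 11/30 v 3/30 gives Fisher p = 0.030; 10/30 v 3/30 gives chi-square p = 0.028 but Fisher p = 0.057. A gap of about 23-27 points is therefore enough, depending on the test.

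**3. Mean catheter days.** Let d be the day of the first repeat VT, p its failure rate, g the retest gap and q the failure rate at each later retest (assumed equal in both arms).

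- Mean days = d + p × g/(1 − q)
- Break-even excess failure in the early arm = (late d − early d) × (1 − q)/g

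Central case (days 3 and 7, g = 6, q = 0): early 3 + 0.41 × 6 = 5.46; late 7 + 0.10 × 6 = 7.60; break-even 4/6 = 67 points.

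| Early d | Late d | g | q | Early mean | Late mean | Break-even (points) |
|---|---|---|---|---|---|---|
| 3 | 7 | 6 | 0 | 5.46 | 7.60 | 67 |
| 3 | 7 | 6 | 0.3 | 6.51 | 7.86 | 47 |
| 2 | 7 | 5 | 0 | 4.05 | 7.50 | 100 |
| 4 | 7 | 7 | 0 | 6.87 | 7.70 | 43 |
| 4 | 6 | 7 | 0 | 6.87 | 6.70 | 29 |
| 4 | 7 | 7 | 0.3 | 8.10 | 8.00 | 30 |

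POD 6 for the late arm comes from the visit table. In the last two rows the order reverses at 41% v 10%. If both extremes apply together, break-even is 2 × 0.7/7 = 20 points. Because Design says on or after POD 7, the late day has no stated upper limit either.

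**4. Assessment day alone.** Suppose recovery is identical and exponential in both arms, with a fraction s not recovered at POD 3 (assumed 20-50%), VTs on days 3 and 7, and a 6-day gap. The failure rates are then s and s^(7/3).

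- s = 0.2: 20% v 2.3%. Mean days 3 + 6(0.2)/(1 − 0.04) = 4.25 v 7 + 6(0.0234)/0.96 = 7.15.
- s = 0.5: 50% v 19.8%. Mean days 3 + 6(0.5)/0.75 = 7.0 v 7 + 6(0.198)/0.75 = 8.6.

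Over s = 0.2, 0.3, 0.4 and 0.5, chi-square at 30 per arm favours late VT 66-73% of the time and Fisher 38-63%. The early arm has the lower mean catheter days throughout.

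**The case against.** The strongest reply is that the protocol states openly that failure rate is its measure of timing, and the SAP agrees. How likely a second VT is to fail at each time is a coherent question, and the test answers it. That stands: this is an objective wider than its endpoint. A reader might infer a concealed outcome switch or an invalid primary test; the documents support neither.

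A reader might also infer that the trial compares nothing else. It does: UTI, later re-insertion, retention and satisfaction are planned, and UTI and satisfaction capture part of the cost of longer catheterisation. None of them measures timing.

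The direction of the primary result is not settled beforehand. Background's statement that earlier removal brings more retention concerns gynaecological surgery in general, and it says the interval after a failed VT has not been studied. An expected direction would also leave the size unknown.

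Finally, catheter days have the mirror-image weakness: the schedule fixes a minimum of 2-4 days v about 7, so they lean towards early VT. That is a fair reason not to let them replace the primary, and to report them only beside it.

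**Conclusion.** The mismatch is in the text and is worth correcting, though it does not undermine the failure-rate test for its narrower question. For the timing objective, one proportion per arm on different days is all that is planned, and it can favour late VT when recovery is the same in both arms. In the central assumed case the early arm loses the primary test with about 82% power (73% by Fisher) while averaging 2.1 fewer catheter days (7.60 − 5.46).

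A reader might infer that early-VT women are always catheter-free sooner. The documents do not support that. The advantage is in the mean; early-arm women who fail wait until about POD 7-11; and under POD 6 late testing, or 30% retest failure with early VT on POD 4 and a 7-day gap, the order can reverse. Nor can it be inferred that the arms are comparable on a like-for-like basis by POD 11: by then an early-arm woman may have had two attempts, while a late-arm woman who failed on POD 7 is not retested before POD 12.

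All failure rates, the retest failure rate and the recovery model are assumptions; only the VT windows, the retest gap and the group size come from the documents.

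**What to change.** - Keep failure of the first repeat VT as primary, with the sample size unchanged. Reword the objective to failure of the first repeat VT at the early v the late time point.
- Add to the SAP, as a named secondary outcome, total catheter days from surgery to 6 weeks, by intention to treat, with a rank-sum test and a difference with 95% CI. Name the rank-sum test explicitly, because the signed-rank test in the SAP is for paired data. State how days on self-catheterisation are counted.
- Report descriptively the cumulative proportion catheter-free by day in each arm, for example at POD 7 and POD 14, with the number of VT attempts each arm has had by then.
- Base any statement on optimal timing on failure rate, catheter days and UTI together.
- Reconcile the late VT day: on or after POD 7 in Design, 7 days in Interventions and Interactions, POD 6-7 in the visit table.

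The cost is one added test, one descriptive display and a few sentences. VT and catheter-removal dates must be confirmed as captured, since neither document says that they are. The SAP is written in the past tense; if results were already known, the added analyses should be labelled as added later.

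### At the stated 10% drop-out, 66 enrolled women leave an expected 59.4 evaluable, marginally below the stated 60; the exact target is 67, or 68 for equal arms

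*Protocol*

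**What the plan says.** The Protocol, Methods and Measures, Design, gives the size needed for the primary comparison: "this study would require 60 subjects, or 30 per group". The next sentence adds the allowance for losses: "Assuming a 10% drop-out rate, 66 total subjects should be enrolled in the study". The inflation formula is not shown.

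The Sample Size item repeats the base figure, "this study will need 60 subjects to be adequately powered", and attributes it to the Fleiss method in OpenEpi and to an earlier randomised trial of catheter duration. It gives no enrolment total after drop-out. The SAP has no sample-size section. Neither document states another enrolment total or another drop-out rate.

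**The concern.** A drop-out allowance is meant to leave the required number of women after the assumed loss. The loss applies to those enrolled, so the required number is divided by one minus the drop-out rate and rounded up. Here the result of 66, put back through the same 10%, falls below the 60 that it was meant to protect.

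The allowance does have work to do in this trial. Under Subject Recruitment Methods, a woman who withdraws may have her collected data removed. The SAP names an intention-to-treat analysis but gives no rule for a missing primary outcome. Nothing in the documents brings a lost woman back into the comparison. What is at stake is whether the plan's stated numbers agree with each other and, to a very small degree, the power at the end.

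**Working it through.** **Inputs**

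- Evaluable women required: 60, or 30 per arm (Protocol, Design; the 60 is repeated under Sample Size).
- Drop-out: 10% (Protocol, Design).
- Enrolment target: 66 (Protocol, Design).
- Power 80% (Protocol); two-sided significance level 0.05 (the Protocol's 95 read together with the SAP's 0.05 threshold).
- Failure rates in the two arms: not given, so assumed below.

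**1. Reproducing 66.** Two routes give it:

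- 60 × 1.1 = 66 exactly.
- 60/0.9 = 66.67, rounded down, = 66.

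The documents do not show which was used.

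**2. Putting 66 back through the stated loss.**

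- 66 × (1 − 0.10) = 59.4 expected evaluable. The shortfall is 60 − 59.4 = 0.6 of a woman, or 1 if 59.4 is rounded down to 59.
- 66 leaves exactly 60 if 6 women are lost: 6/66 = 9.1%.

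**3. Exact inflation.**

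- Total: 60/(1 − 0.10) = 66.67, rounded up to 67. Check: 67 × 0.9 = 60.3.
- Per arm: 30/0.9 = 33.3, rounded up to 34, so 68 in total. Check: 68 × 0.9 = 61.2.

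The stated target is short by 1 woman, or by 2 with equal arms.

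**4. Chance of ending with at least 60.** Assume that each woman drops out independently with probability 0.10. The number evaluable is then binomial with success probability 0.90:

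| Enrolled | P(at least 60 evaluable) |
|---|---|
| 66 | 0.51 |
| 67 | 0.65 |
| 68 | 0.76 |

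**5. Effect on power.** I took later-group failure rates from 2% to 30% and paired each with the early-group rate at which the Fleiss formula gives 30 per arm. Power is Φ[(|p1 − p2| − 1.96 × SE0)/SE1], where SE0 uses the pooled proportion and SE1 the separate ones. It is evaluated at 30 per arm and at 29.5 per arm (59 in total). Without continuity correction in the sizing:

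| Later rate (assumed) | Early rate giving 30 per arm | Power, 60 women | Power, 59 women |
|---|---|---|---|
| 2% | 27.0% | 80.1% | 79.4% |
| 10% | 40.9% | 80.0% | 79.3% |
| 20% | 54.3% | 80.1% | 79.4% |
| 30% | 65.5% | 80.1% | 79.4% |

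For the 10% row, SE0 = √(0.2545 × 0.7455 × 2/30) = 0.1125 and SE1 = √((0.409 × 0.591 + 0.10 × 0.90)/30) = 0.1052. This gives (0.309 − 1.96 × 0.1125)/0.1052 = 0.84 and Φ = 0.80.

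The loss is about 0.7 points throughout. If the sizing used the continuity correction, which the Protocol does not say, the paired rates lie further apart and the loss is 0.5 to 0.6 points.

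**6. Exact check at one assumed pair.** For the Pearson test at 40% against 10%, exact power is 79.6% with 30 + 30. With 59 women it is 79.4% if the missing woman is in the 10% arm and 79.6% if she is in the 40% arm. This pair does not give the Protocol's 30 per arm (the Fleiss formula gives 32, or 38 with continuity correction), so it serves only as an illustration.

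**The case against.** The strongest reply is that this is rounding. Both 60 and 10% are round planning figures, and a drop-out rate stated as a whole percentage hardly separates 10% from the 9.1% at which 66 is exactly enough. At a true 10% loss, 66 still leaves 60 or more about half the time, and 67 guarantees nothing either. The base of 60 cannot itself be checked, because the failure rates behind it are not given, so the correction adds precision to an unverified number.

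Most of this stands, and it sets the size of the point. It does not make the sentence correct: the allowance is stated at 10%, and at 10% the expected yield is below 60. The missing failure rates are a separate and larger gap, and they do not affect a check that uses only the stated 60, 10% and 66.

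A reader might infer three stronger things, and the documents support none of them.

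- That the authors multiplied by 1.1 where they should have divided by 0.9. The figure matches that, but it also matches 66.67 rounded down, and no formula is shown.
- That the power claim depends on 66. Both places that state the power attach it to 60.
- That the trial is left underpowered by this. The change is under 1 point, and at the one pair checked exactly it depends on which arm loses the woman, so part of it is discreteness of the test.

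Whether the 66 counts consented or randomised women is a different question. Consent is signed before the qualifying voiding trial, and the documents do not define enrolment. That lends no weight to the arithmetic here.

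**Conclusion.** The point holds as a minor correction. The stated enrolment figure is slightly inconsistent with the stated requirement and drop-out rate: by 0.6 of a woman in expectation, and by 1 or 2 women in the target. That part follows from the Protocol's own numbers, reading the 10% as a loss from those enrolled. The power cost of about 0.5 to 0.7 points rests on assumed failure rates and a normal-approximation formula, but it hardly varies over the range tried. No conclusion of the trial would turn on it.

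**What to change.** In the Protocol's Design section, do one of the following:

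- keep 66 and add that it is expected to leave about 59 evaluable women at 10% drop-out, or 60 at about 9%; or
- change the target to 67, or to 68 if the arms are to be equal at 34 each.

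Showing the formula beside the figure would settle how it was reached. The first option costs one sentence and no extra women. The second costs one changed figure and one or two more women. Neither alters the design or the analysis.

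### Two centres, one joining after more than 30 enrolments, but no site-stratified allocation is described and the primary test has no site term: a loss of precision that a stratified analysis would recover at almost no cost

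*Protocol*

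**What the plan says.** The Protocol's Setting section states: "The study will take place at two medical centers". The Sample Size section adds that the coordinating centre is already recruiting and gives the hoped-for contribution of the other: "Over 30 patients are already enrolled at that site. Ideally, 20 subjects would be enrolled from Wake Forest Baptist Health in North Carolina". The planned total is 60 women, 30 per arm, raised to 66 for dropout.

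The Design section gives randomisation one clause: "the subject will be called on POD#1 and randomized to either the early voiding trial group (EVT) or the late voiding trial group (LVT". It does not describe how the sequence is generated, or any blocking or stratification.

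On outcome assessment, the same section says that "the patient will be given a standardized voiding trial as per the usual protocol". The content of that usual protocol is not set out in the text available, and the Appendix shows only its heading. Interventions and Interactions leaves antibiotic prophylaxis to the surgeon. Urine culture follows usual practice, but with a stated trigger and a stated colony threshold.

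The SAP says: "Categorical data, such as void trial failure rates (the primary outcome), were analyzed using Pearson's chi-square test", with Fisher's exact test for sparse cells. It also lists a forward stepwise multivariate regression without naming covariates. Site is not mentioned in the SAP, nor among the items that the Protocol names for checking that the groups are equivalent (an open-ended list).

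**The concern.** The recovery-room VT decides who enters the trial, and the office VT supplies the primary outcome. If the two centres differ in case mix, surgery or the way the VT is run, their failure rates will differ. About 20 of 60 to 66 women are expected from the late-joining centre, so the arms could by chance hold unequal shares of them, and part of any centre difference would then sit in the early-versus-late contrast.

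A pooled test neither removes that component nor shows whether the timing effect agrees across centres. In a trial this small, any avoidable noise in the primary comparison matters. The same applies to UTI, where prophylaxis at the surgeon's discretion is a further route to a centre difference.

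**Working it through.** **Inputs from the documents.** Two centres; more than 30 women at the first; 20 hoped for at the second; 60 women (30 per arm), 66 with dropout; two-sided 5% level; pooled chi-square or Fisher test.

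**Assumptions.** Second-centre share of 20/60 or 20/66 (more than 30 plus 20 exceeds only 50, so either total needs the first centre to keep enrolling). Site gap in failure rate of 10, 20 or 30 points, equal in both arms. The documents give no failure rates, so those used below are also assumed.

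**The plan's own figure.** 60 × 1.10 = 66 reproduces the enrolment target. The 60 itself cannot be reproduced, because the two failure rates behind it are not stated.

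**Step 1: chance of imbalance among 20 second-centre women.** The allocation method is not described, so two models are shown.

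| Split or worse | Fixed arms, 30+30 (hypergeometric) | Fixed arms, 33+33 (hypergeometric) | Simple randomisation, Binomial(20, 0.5) |
|---|---|---|---|
| 13:7 | 17.0% | 18.0% | 26.3% |
| 14:6 | 5.4% | 5.9% | 11.5% |

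The shifts in Step 2 assume 33 per arm, so the matching probabilities are 18% and 6%.

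**Step 2: shift in the crude difference.** Shift = site gap × (second-centre share in one arm − share in the other).
- 13:7 at 33 per arm: (13 − 7)/33 = 0.182. Gaps of 10, 20 and 30 points give 1.8, 3.6 and 5.5 points.
- 14:6 at 33 per arm: (14 − 6)/33 = 0.242. The same gaps give 2.4, 4.8 and 7.3 points.

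**Step 3: compare with sampling error.** SE = √[p₁(1−p₁)/n + p₂(1−p₂)/n].
- 30% in both arms: 11.8 points at n = 30, 11.3 at n = 33.
- 20% in both arms: 10.3 points at n = 30, 9.8 at n = 33.

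The largest shift shown, 7.3 points, is below one SE.

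**Step 4: type I error of the pooled chi-square** (100,000 simulated trials per setting, 40 + 20 women, 30 per arm, 20% or 30% overall failure, gaps 0-30 points).
- Allocation ignoring site: 0.047-0.049, with average shift zero.
- Allocation stratified by site, 30-point gap: 0.038 at 30% failure and 0.035 at 20%. The test is conservative because its variance still contains the site component that the design has removed.
- Conditional on a realised 14:6 split at 30% failure: 0.067 at a 20-point gap and 0.089 at 30 points. Conditional on 13:7: 0.057 and 0.066. The excess rejections favour one direction.

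**Step 5: what a site-stratified Cochran-Mantel-Haenszel (CMH) test changes.** Failure rates of 45% v 12%, allocation ignoring site:

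| Site gap | Pooled power | CMH power | Change |
|---|---|---|---|
| 0 | 0.836 | 0.831 | −0.5 points |
| 10 points | 0.836 | 0.836 | 0 |
| 20 points | 0.837 | 0.853 | about +1.7 points |
| 30 points | 0.837 | 0.882 | +4.5 points |

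Across the other settings run (50% v 15%, and site-stratified allocation), the gain is 1.5 to 4.0 points at gaps of 20-30 points. Type I error of the CMH test stays at 0.048-0.050 across settings.

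**The case against.** The strongest reply is that randomisation already covers this. A chance imbalance averages to zero, is part of the pooled test's sampling error, and leaves its unconditional type I error at or just below 5%. That is correct, and a reader who inferred that the plan is biased by centre would be wrong. What remains is that a single trial must live with the split it gets, and that the pooled test ignores information already held.

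A reader might also infer that each centre follows its own practice. The documents do not say so. They call the voiding trial standardized, and they give a trigger and threshold for culture. Only prophylaxis is expressly left to the surgeon, and the documents do not link it to VT failure. What they support is that outcome rates may differ, because the protocol referred to is not set out in the text available.

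A third tempting reading is that randomisation was not stratified by site. The text is silent, so stratification is unreported rather than absent. This does not rescue the pooled test: if allocation was stratified, that test is conservative.

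Finally, the stepwise regression could admit site. But site is not named as a candidate, its entry would depend on the data, and the regression is not stated to be the primary comparison.

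**Conclusion.** The point holds as a matter of efficiency and reporting, not as a threat to validity. The plan has two centres, one joining late, and a primary test that takes no account of site. Under the assumed 10-30 point site gap, a 13:7 or 14:6 split moves the estimate by about 2-7 points, less than one standard error, and with fixed arms a split of 13:7 or worse occurs about one time in six. Either possible reading of the silence on allocation leads to the same place: unstratified allocation leaves recoverable noise, and stratified allocation makes the pooled test conservative.

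The size rests on the assumed site gap, the assumed failure rates and about 20 women at the second centre, none of which the documents fix. If the centres have similar failure rates, the effect is negligible.

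**What to change.** - Make the primary comparison of VT failure, and the UTI comparison, site-stratified: a CMH test, or an exact stratified test if cells are sparse, with a Mantel-Haenszel risk difference and confidence interval.
- Tabulate failure by arm within each centre, so that consistency can be seen. With about 20 women at one centre this is descriptive only.
- State how the allocation sequence was generated and whether it was stratified by site.
- If allocation at the second centre has not begun, give it its own blocked list.

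The SAP is written in the past tense, so the last step may no longer be possible. The stratified analysis and the table do not depend on it and need only the site identifier. The cost is at most about half a point of power if the centres do not differ, against a gain of about 1.5-4.5 points at assumed gaps of 20-30 points.
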